### 4.4 SUBJECT SELECTION CRITERIA

Assessment of eligibility is based on data available to the Investigator at the time of subject enrollment.

Patients with symptomatic peripheral arterial disease (Rutherford Becker Class II to IV) will be enrolled if they have been previously treated with stenting in the femoropopliteal segment and now return with suspicion of restenosis. There is no limit on how many times the target in-stent restenotic lesion has been previously treated. Also there is no exclusion based on how the prior treatment was done including if drug eluting balloons or stents have been used. Covered stents cannot be included however including Viabhan stents. There is no limit on the length of the target lesion as long as only one target lesion is treated and enrolled. If there is more than one target lesion per vessel, this will be considered an exclusion. Patients will be considered enrolled in the study following the index angiogram and if they are deemed by the operator to meet the inclusion criteria and none of the exclusion criteria and prior to commencement of any therapeutic intervention. In this study, and in order to ensure adequate representation of minority and ethnic groups affected by PAD, our target for the Black population will be about 15% of all patients enrolled and for females a minimum of 30%

#### 4.4.1 INCLUSION CRITERIA

Subjects must meet all of the following criteria to be eligible to participate in this study:

- 1. Subject is 18 years of age or older.
- 2. Subject presents with clinical evidence of peripheral arterial disease with ISR in the femoropopliteal segment (includes common femoral, superficial femoral and popliteal)
- 3. Subject presents with a Rutherford Classification of 2-4 and has symptoms of rest limb pain or claudication.
- 4. Target lesion(s) must be viewed angiographically and have  $\geq$ 50% stenosis.

- 5. The atherectomy wire must be placed entirely across all lesions to be treated with no visible evidence of clear or suspected subintimal/substent wire passage.
- 6. The main target vessel reference diameter must be  $\geq 5 \text{ mm}$  and  $\leq 7 \text{ mm}$
- 7. One patent distal run-off vessel with <70% disease and with brisk flow is required.
- 8. Intraluminal crossing of the lesion. If this is not certain, IVUS may be used to verify this per operator's discretion
- 9. Patient has signed approved informed consent.
- 10. Patient is willing to comply with the follow-up evaluations at specified times.

#### 4.4.2 EXCLUSION CRITERIA

Subjects will not be eligible to participate in the study if any of the following conditions are present:

- 1. Subject is unable to understand the study or has a history of non-compliance with medical advice.
- 2. Subject is unwilling or unable to sign the Informed Consent Form (ICF).
- 3. Subject is currently enrolled in another clinical investigational study that might clinically interfere with the current study endpoints
- 4. Subject is pregnant or planning to become pregnant within the study period.
- 5. Subject has a known sensitivity to contrast media and the sensitivity cannot be adequately pre-medicated for.
- 6. Subject is diagnosed with chronic renal failure or has a creatinine level > 2.5 mg/dl and is not on chronic dialysis.
- 7. Subject has a known allergy to heparin, ASA, Plavix.
- 8. Subject has a history of bleeding disorders or platelet count < 80,000 cells/ml.
- 9. Subject experiences ongoing cardiac problems (e.g., cardiac arrhythmias, congestive heart failure exacerbation, myocardial infarction, etc.) that, per the investigator, would not make the subject an ideal candidate for study procedures.
- 10. Subject has a CVA or TIA within 4 weeks prior to JetStream procedure.
- 11. Subject has an anticipated life span of less than 12 months.
- 12. Subject is suspected of having an active systemic infection.
- 13. Limited vascular access that precludes safe advancement of the Jetstream XC System to the target lesion(s).
- 14. Patient has evidence of intracranial or gastrointestinal bleeding within the past 3 months.
- 15. Patient has had severe trauma, fracture, major surgery or biopsy of a parenchymal organ within the past 14 days.
- 16. Patient has any planned surgical intervention or endovascular procedure  $\leq$  30 days after the index procedure.
- 17. Use of another debulking device during the index procedure prior to the Jetstream XC System.
- 18. Use of another debulking device after the Jetstream XC system.
- 19. Class III and IV fractures
- 20. Stents not fully apposed to vessel wall or overlapping stent segments

21. Target lesion previously treated with a covered stent (such as Viabhan stent)

#### 4.43 STUDY TREATMENT RULES

- 1. No other debulking devices, cutting/scoring balloons or cryogenic balloons may be used in before or after the Jetstream XC
- 2. Balloon inflation is per operator's discretion but should not exceed burst pressure and should be at least at nominal pressure. Operators should increase balloon pressure beyond nominal pressure only if balloon full expansion does not occur at nominal pressure. If higher balloon pressure beyond nominal is felt necessary, then pressure is increased at 1 atm every 5 seconds until full balloon expansion occurs.
- 3. Semi-compliant balloons are recommended
- 4. The only adjunctive therapies allowed are PTA and bailout stenting:
  - Bailout stenting is allowed if > 30% residual stenosis remains or for perforation
  - Type D dissection leading to flow limitations
  - Self-expanding nitinol stents are recommended if needed
  - Covered stents are allowed only if there is a perforation
  - Bailout stenting is not allowed if the lesion has ≤ 30% residual stenosis
  - Only one leg may be treated per patient. Patient is enrolled only once in the study.
  - Drug coated stents or Drug coated balloons are not allowed.

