### 4.2 PRIMARY OUTCOME

### Effectiveness

**Target Lesion Revascularization (TLR) at 6 months**: TLR is defined as retreatment of the index lesion (extended 1 cm proximal and distal to the lesion) at 6 months. For the primary endpoint, intra-procedural bail out stenting of the index lesion is considered meeting a TLR endpoint. (Intention to treat Analysis analysis)

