#### 4.644 ADJUNCTIVE PROCEDURES

Adjunctive procedures besides PTA should be avoided if possible. In the event of a major flow limiting dissection (type D and higher), perforation, or occlusive complication (e.g., recoil), prolonged balloon inflation (5 minutes) must be attempted first. All efforts should be made to eliminate the need for bail-out stent placement. In cases where the results after prolonged balloon inflation are suboptimal, bail-out stenting is allowed. A cine following the prolonged balloon inflation must be captured; all bail-out stenting procedures will be reviewed by the Angiographic Core Laboratory. Adjunctive treatment with cutting balloons or scoring balloons is not allowed. Adjunctive or primary PTA should be done with a non-compliant or semi compliant balloon sized 1:1 to vessel size. Adjunctive stenting is performed only with self-expanding nitinol stent. Drug coated stents, covered stents, or drug coated balloons are not allowed in the study.

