### **12.0 DEFINITIONS**

**Abrupt Closure:** Vessel occlusion at the site of treatment within 24 hours after successful index procedure.

Access Site Complications: Adverse sequelae at the access site as a result from cathether-based interventions, including arterio-venous fistula, bleeding, hematoma, infection and pseudoaneurysm.

**Adjunctive Treatment:** A procedure performed after treatment with the protocol-defined treatment (JS + PTA) to treat major flow limiting dissection (grade D or greater), perforations, occlusive complications (i.e. recoil) or residual stenosis greater than 30% in the target lesion.

Adverse Event: Any untoward and unintended clinical sign, symptom, or disease in a subject. This definition does not imply that there is a relationship between the adverse event and the device under investigation.

Serious Adverse Event (SAE)	Serious Adverse Event: Any adverse events that led to a death or led to a serious deterioration in the health of the subject that 1) resulted in a life-threatening illness or injury, 2) resulted in a permanent impairment of a body structure or a body function, 3) required inpatient hospitalization or prolongation of existing hospitalization, or 4) resulted in medical or surgical intervention to prevent permanent impairment to a body structure or body function. This definition also includes any adverse event that led to fetal distress, fetal death or a congenital abnormality or birth defect.
Major Adverse Events	Major Adverse Events (MAE) as individual endpoints in-hospital and up to 30 days : Include device-induced vascular injury as reported by the operator, amputation (major and minor unplanned), death, significant distal embolization requiring the use of pharmacologic or mechanical means to treat (other than a vasodilator), perforation (extravasation of blood outside the vessel wall), major bleeding, non- fatal myocardial infarction (defined as the occurrence of more than 20 minutes of chest pain post procedure with an increase in troponin), stroke, access complications (AV fistula and pseudoaneurysm), bail out stenting, acute renal failure (drop in crcl by > 25% from baseline), acute ( $\leq$ 24 hours) or subacute ( $\leq$ 1 month , > than 24 hours) vessel closure. Major Adverse Events (MAE) as composite endpoint at 30 days: unplanned amputation (major or minor), death or TLR at 30 days (TLR includes bail out stenting)
	Major Adverse Event Rate as individual and composite endpoint at

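### For a perforation or flow-limiting type D dissection with residual stenosis of 30% or less, section 4.43 both permits and forbids a bailout stent, and each such stent is a primary-endpoint event

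*Combined protocol and SAP*

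**What the plan says.** Four places in the protocol govern bailout stenting.

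- **Section 4.43 (Study Treatment Rules).** The permissive bullets read "Bailout stenting is allowed if > 30% residual stenosis remains or for perforation" and then "Type D dissection leading to flow limitations". A later bullet in the same list reads "Bailout stenting is not allowed if the lesion has ≤ 30% residual stenosis". No exception is given. On stent type, the list says "Covered stents are allowed only if there is a perforation".
- **Section 4.643 (JS + PTA Group Procedures).** Treatment of a complication during JetStream (JS) use is left to the operator, and a perforation in the treated area has to be sealed.
- **Section 4.644 (Adjunctive Procedures).** For flow-limiting dissection of type D or higher, perforation or occlusive complication, a prolonged balloon inflation comes first. Then: "In cases where the results after prolonged balloon inflation are suboptimal, bail-out stenting is allowed". No residual-stenosis threshold appears. The section closes with "Drug coated stents, covered stents, or drug coated balloons are not allowed in the study".
- **Section 12.0 (Definitions), Adjunctive Treatment.** After dissection of grade D or greater, the triggers continue as "perforations, occlusive complications (i.e. recoil) or residual stenosis greater than 30% in the target lesion", so the complications stand as alternatives to residual stenosis.

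Section 4.2 ties these rules to the primary endpoint: "intra-procedural bail out stenting of the index lesion is considered meeting a TLR endpoint". The 30-day major adverse event (MAE) composite also includes bailout stenting. The DSMB row of the Synopsis sets a stopping threshold of 78% freedom from MAE after 60 patients. None of the changes listed at the end of the document touches the bailout rule.

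**The concern.** A bailout stent normally follows from a treatment decision and is not itself an outcome. Here the decision to stent is the event. If the rule for that decision contradicts itself, two sites facing the same complication can both follow section 4.43 and record different primary outcomes. One places a stent and scores a TLR on day 0. The other withholds it and scores nothing unless the lesion is retreated later.

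The study has one arm, up to 14 sites and a fixed historic comparator, so randomization does not balance differences in how sites read the rule. The effect could go either way: a strict reading lowers the event count and a permissive one raises it. The conflict also concerns what operators may do during a complication, so it touches patient safety as well as the estimate.

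**Working it through.** **1. The rules side by side.** Each row is a situation after JS and balloon angioplasty.

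| Situation | 4.43, permissive bullets | 4.43, prohibition | 4.644 | 12.0, Adjunctive Treatment |
|---|---|---|---|---|
| No complication, residual >30% | allowed | does not apply | not addressed, unless from recoil | included |
| No complication, residual ≤30% | no trigger | forbidden | not addressed | not included |
| Perforation or flow-limiting type D dissection, residual >30% | allowed | does not apply | allowed if suboptimal after inflation | included |
| Same complication, residual ≤30% | **allowed** | **forbidden** | allowed if suboptimal after inflation | included |

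Only the last row is contradictory. Three smaller mismatches accompany it:
- Section 4.43 has no inflation step, while 4.644 requires one.
- Section 4.43 names type D only, while 4.644 and 12.0 say D or above.
- Covered stents are permitted for perforation in 4.43 and excluded in 4.644.

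**2. The plan's own sample size.** Inputs from section 5.12: control rate 0.38, JS rate 0.21, alpha 0.05 (taken as two-sided), power 0.80, uncorrected chi-squared, 1:1. With mean rate 0.295:

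n = [1.960·√(2·0.295·0.705) + 0.842·√(0.38·0.62 + 0.21·0.79)]² / 0.17² = (1.264 + 0.533)² / 0.0289 = 111.8, so 112 per group.

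The stated figure reproduces, and nothing in this point disputes it.

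**3. How many events decide the test.** Appendix A gives 69/182 control events. With 112 JS patients, χ² = (difference in proportions)² / [p̄(1−p̄)(1/112 + 1/182)], where p̄ is the pooled proportion:
- 30/112 (26.8%): χ² = 3.843, p = 0.04995
- 31/112 (27.7%): χ² = 3.235, p = 0.072

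Success therefore needs at most 30 JS events. One stent moves the rate by 1/112 = 0.9 points.

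**4. Illustration of sensitivity.** The number of disputed stents, k, is an assumption; the documents do not give it. With X ~ Binomial(112, p) and the control held at 69/182, the chance of success is P(X ≤ 30 − k):

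| True JS rate p | k = 0 | k = 2 | k = 4 |
|---|---|---|---|
| 0.21 | 0.944 | 0.875 | 0.759 |
| 0.25 | 0.712 | 0.551 | 0.378 |

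The 0.944 exceeds the planned 0.80 because the control is treated as fixed and has 182 patients. At the planned maximum of 140 patients the critical count is 38 (p = 0.042; 39 gives p = 0.058). At p = 0.21 the chances are then 0.967, 0.927 and 0.855.

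**5. The stopping threshold.** Among 60 patients, 13 MAEs leave 47/60 = 78.3% event-free and 14 leave 46/60 = 76.7%. One stent can put the result on either side of 78%.

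**The case against.** The best defence is that the prohibition is only the mirror image of the >30% criterion and was never meant to cover complications. Much supports that reading. Section 12.0 lists complications as alternatives to residual stenosis. Section 4.643 leaves complications to the operator. The covered-stent bullet in 4.43 presupposes that perforations may be stented. Section 4.644 can be read as adding a step to the complication branch, where no stenosis threshold would be expected. On that view all that is missing is a short qualifier. This stands as a plausible account of intent, but the text does not state it. The prohibition is unqualified, and the disagreement over covered stents remains on any reading. The section 12.0 definition is also only indirect support, since it describes adjunctive procedures and does not name stenting.

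The size is also open to challenge. Appendix A reports 2 bailout stents in 29 limbs, both for suboptimal results and neither attributed to perforation or dissection. At that rate 112 patients would have 112 × 2/29 = 7.7 bailouts, so two to four more is an increase of roughly a quarter to a half. The illustration further assumes that every disputed stent adds to the base rate and that none of those patients would have had a TLR by 6 months anyway. This objection stands: the power figures show sensitivity and predict nothing.

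Section 4.644 already requires a cine after prolonged inflation and core-laboratory review of every bailout. That lets reasons be reconstructed, but the plan does not say that the indication will be recorded.

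**Conclusion.** The contradiction is real and confined to one group: lesions with perforation or flow-limiting type D dissection and residual stenosis of 30% or less. It should be corrected because the rule creates primary-endpoint events and 30-day MAEs, and because operators have to apply it during a complication. The size of the group is unknown. The fall from 0.94 to 0.87 or 0.76 (0.97 to 0.93 or 0.85 with 140 patients) rests on an assumed two to four extra events at a true rate of 21%, a fixed control of 69/182 and complete follow-up.

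Two stronger readings are not supported. A reader might infer that the primary endpoint itself is ill-defined. It is not: any intra-procedural bailout stent in the index lesion counts, and the residual-stenosis branch of the rule is unambiguous. A reader might also infer that this conflict is what prevents the JS bailout rate from being matched to the 7 to 20% quoted for the balloon arms in the Synopsis. That does not follow. The bailout rules of the control trials are not in the documents, so even a perfectly worded rule here could not be shown to match them. That is a limit of the historic control.

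**What to change.** Reconcile sections 4.43, 4.643, 4.644 and the Adjunctive Treatment definition in 12.0 into one consistent list of bailout indications. It should state how residual stenosis and complications relate, whether prolonged inflation comes first, which dissection grades qualify and whether covered stents may be used for perforation. The content is for the sponsor's clinicians to decide; the statistical requirement is that one list applies at every site.

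Have the core laboratory record the indication for each bailout stent as part of the review already planned, and report the primary endpoint by reason for bailout alongside the overall rate. The cost is protocol wording and one case report form field. The sample size and the primary test do not change.

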#### 4.44 GENERAL EXCLUSION CRITERIA

The subject must not meet any of the following general exclusion criteria.

- 1. Has one or more of the contraindications listed in the JetStream IFUs.
- 2. Patient has already been enrolled once in the protocol
- 3. Has a contraindication or known untreated allergy to antiplatelet therapy, anticoagulants, thrombolytic drugs or any other drug anticipated to be used (that cannot be reasonably substituted).
- 4. Has known hypersensitivity to treatment device materials including nitinol.
- 5. Has known uncontrollable hypercoagulable condition, or refuses blood transfusion.
- 6. Has surgical or endovascular procedure of the target or non-target vessel within 30 days prior to the index procedure.
- 7. Has had a previous peripheral bypass affecting the target vessel (allowable for physician to pass through bypass graft in aorta-iliac region to get to the target lesion).
- 8. Has had superficial thrombophlebitis or deep venous thrombus within 30 days prior to index procedure.

- 9. Has history of significant gastrointestinal bleeding in the past 1 month prior to index procedure, or any history of hemorrhagic diathesis.
- 10. Patients with ipsilateral Iliac and CFA disease are allowed in the study but these lesions have to be treated successfully first (<30% residual) before patient can be enrolled. Treatment as per investigator's preference.
- 11. Lesions have to be separated by > 5 cm in order to be considered different lesions. Only one lesion per target vessel can be enrolled during the index procedure

#### 4.45 **PATIENT SCREENING**

It is recommended that all eligible patients be approached for enrollment in the study and be screened at the study site. Study personnel will explain to the patient that even if the patient agrees to participate in the study and signs the written informed consent, angiography may demonstrate that the patient is not a suitable candidate for the study.

#### 4.46 SUBJECT ENROLLMENT

The subject is enrolled in the study after he/she has signed the subject informed consent and it has been determined that he/she meets all of the inclusion criteria and none of the exclusion criteria. The point of enrollment is defined as the moment an exchangeable guidewire and treatment catheter cross the target lesion in the true lumen.

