#### INTENDED USE

The JS device catheter is intended for use in peripheral arterial intervention to treat denovo and non-stent restenotic infrainguinal lesions. JS is not intended for use in the coronary, carotid, iliac or renal vasculature.

JS application in treating FP ISR is off label and considered investigational

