### **2.0 DEVICE DESCRIPTIONS**

#### JETSTREAM XC ATHERECTOMY DEVICE

The Boston Scientific Jetstream XC catheter is a rotating, aspirating, expandable catheter for active removal of atherosclerotic disease and thrombus in peripheral vasculature. The JS XC System has been cleared by the FDA for use in the peripheral vasculature to treat denovo and non-stent infrainguinal lesions

JETSTREAM XC™ device has 2 sets of blades: one set is at the tip of the catheter and the other (5 blades) is mounted proximal to the tip. Counterclockwise rotation expands the proximal blades and allows wider tissue cutting. The JetStream Navitus has been improved compared to its predecessor, the Pathway device, with the aspiration port placed proximal to the blades instead of distally, allowing a more robust aspiration capacity. The recommended use of this device with tips and tricks on how to operate it can be found in prior publications.

There are 2 cutter designs with the JETSTREAM device. The JETSTREAM® XC (or eXpandable Cutter Catheters) and the JETSTREAM® SC (or Single Cutter Catheters). The Expandable Cutter, as the name implies, can be used blades down (BD) and blades up (BU) with single insertion and are for femoropopliteal vessels. The XC or Expandable Cutters Catheters come in 2 sizes: 2.1mm/3.0mm (135 cm length) is best suited for vessel size larger than 3.0 BD and 4.0-5.0 mm BU; and the 2.4mm/3.4mm (120 cm length) is typically used for vessels 4.0-4.9mm BD and 5.0 mm or larger BU. Also, the SC or Single Cutter Catheters come in two sizes: 1.6 mm (145 cm length) best suited for vessel size 2.0-2.5 mm; and the 1.85 mm (145 cm shaft length) typically used for vessel sizes 2.6-3.0 mm. The single cutters have only have a front end cutter with no BU feature and typically are used for proximal and mid tibial and peroneal vessels. The device is retracted through the treatment area by "rexing" it until wire loop is back to its initial size.

http://www.bostonscientific.com/content/dam/bostonscientific/pi/portfoliogroup/Catheters%20Atherectomy/JetStream/Resources/4137-

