#### 4.62 ANGIOGRAM

A sheath will be inserted and after insertion the subject should receive anticoagulation medications as indicated by the Investigator to maintain appropriate clotting time. Selective angiography of the limb to be treated including the distal aorta, bilateral iliac, ipsilateral femoral, popliteal and tibial-peroneal vessels (to the pedal level) will be performed to identify the anatomical characteristics of the vasculature and to best isolate and define the lesion. If a pre-procedure assessment has been completed with CTA/MRA, the angiography can be limited to the target vessel, with a baseline assessment of run-off. Angiography must be conducted according the Angiographic Protocol (refer to Core Lab requirement). Gadolinium and CO2 are not allowed for use as contract material.

During angiography the Investigator performing the procedure will assess the subject for the angiographic inclusion and exclusion criteria. It is required that a radiopaque ruler be used to define lesion length and define anatomical measurement references. If the subject meets all the angiographic inclusion criteria and does not meet any of the angiographic exclusion criteria, the subject is enrolled when an exchangeable guidewire crosses the target lesion. Upon enrollment, subjects will be then treated with the JS + PTA as per protocol.

Angiographic films, including run-off, will be obtained immediately prior to and after treatment (after JS alone, and after adjunctive PTA or bail out stenting) according to the Angiographic Core Lab Protocol. Capture images that demonstrate the stenosis in two views that minimize the degree of vessel overlap and demonstrate the stenosis in its most severe view. Angiographic results must be sent to the Angiographic Core Laboratory.

The Angiographic Core Laboratory assessments will supersede the measurements by the Investigator performing the procedure for data analysis purposes; however, the measurements by the Investigator performing the procedure will be used to determine subject eligibility at the time of enrollment.

The Angiographic core laboratory will also assess stent fracture location and severity at baseline prior to any treatment and post atherectomy to assess for additional/worsening fractures.

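### The enrolment point is stated in conflicting ways, and on one reading patients in whom JetStream is tried but does not cross are never enrolled and leave both primary rates

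*Combined protocol and SAP*

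**What the plan says.** The combined protocol and SAP places enrolment at three different moments.

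- **Guidewire and treatment catheter across the lesion.** Section 4.46: "The point of enrollment is defined as the moment an exchangeable guidewire and treatment catheter cross the target lesion in the true lumen". Section 4.641 and the Enrollment entry in section 12.0 repeat the sentence.
- **Guidewire across the lesion.** Section 4.62: "the subject is enrolled when an exchangeable guidewire crosses the target lesion". The next sentence gives the order: "Upon enrollment, subjects will be then treated with the JS + PTA as per protocol".
- **Before therapy.** Section 4.4 enrols after the index angiogram, once the operator judges the patient eligible, and "prior to commencement of any therapeutic intervention".

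The last two select nearly the same patients, because inclusion criterion 5 already demands that "The atherectomy wire must be placed entirely across all lesions to be treated".

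The term treatment catheter is not defined in section 12.0 or elsewhere. The Intended Use paragraph states "The JS device catheter is intended for use in peripheral arterial intervention", and section 2.0 says the "Jetstream XC catheter is a rotating, aspirating, expandable catheter".

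Section 4.2 specifies an intention-to-treat (ITT) analysis of 6-month TLR, and "For the primary endpoint, intra-procedural bail out stenting of the index lesion is considered meeting a TLR endpoint". The 30-day MAE endpoint adds amputation and death and names no analysis set. Sections 5.23 and 5.25 repeat ITT, and 5.23 adds an analysis by actual treatment. Neither set is described.

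**The concern.** A single-arm study has no randomisation to fix who belongs in the ITT analysis. The enrolment point does that job, so it has to be unambiguous and should come before the device can fail.

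Suppose a site takes the treatment catheter to be the JS catheter. A patient whose lesion the wire crosses, but in whom JS is tried and does not cross, is then not enrolled under 4.46, 4.641 and 12.0. The same patient is enrolled under 4.62 and 4.4. Under the first rule, that patient's later events count in neither primary rate. The result is compared with a fixed external figure of 69/182 (Appendix A), so losing patients who fail more often than the rest would favour JS. Patients who were never enrolled have no study follow-up, so the loss could not be repaired at analysis.

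**Working it through.** **The plan's own figure.** Section 5.12 uses 0.38 against 0.21, power 0.8, alpha 0.05, an uncorrected chi-squared test and a 1:1 ratio. With mean rate 0.295 and a two-sided test:

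n = [1.96√(2 × 0.295 × 0.705) + 0.842√(0.38 × 0.62 + 0.21 × 0.79)]² / 0.17² = 111.8, so 112 per group.

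This reproduces the plan's number. The point below changes no stated figure.

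**Inputs from the documents**
- Comparator: 15/44 + 15/57 + 39/81 = 69/182 = 37.9% (Appendix A).
- JS rate: (2 bailout stents + 4 TLR)/29 = 20.7% (Appendix A).
- Maximum enrolment: 140 (section 5.23).

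**Assumptions**
- f is the share of wire-crossed patients in whom JS does not cross. No value is given; 2%, 5% and 10% are tried.
- q is the event rate in those patients. The documents' nearest anchor is the balloon-angioplasty rate of 37.9%, since angioplasty with bailout stenting is the other therapy that section 4.43 allows. Values of 50%, 75% and 100% are a sensitivity range without a source.
- r, the rate in the remaining patients, is taken as 20.7%.

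**Shift in the JS rate.** The wire-crossed set has rate (1 − f)r + fq and the catheter-crossed set has rate r. The catheter rule therefore lowers the rate by f(q − r). In percentage points:

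| q | f = 2% | f = 5% | f = 10% |
|---|---|---|---|
| 37.9% | 0.3 | 0.9 | 1.7 |
| 50% | 0.6 | 1.5 | 2.9 |
| 75% | 1.1 | 2.7 | 5.4 |
| 100% | 1.6 | 4.0 | 7.9 |

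For example, 0.05 × (0.379 − 0.207) = 0.0086.

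**Effect at the planned rate.** These are two-sided uncorrected chi-squared tests against 69/182 with 140 analysed. The catheter-crossed set gives 0.207 × 140 ≈ 29 events, p = 0.0009. The wire-crossed set gives:

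| f, q | Events/140 | p |
|---|---|---|
| 10%, 37.9% | 31 | 0.0024 |
| 5%, 50% | 31 | 0.0024 |
| 5%, 100% | 35 | 0.014 |
| 10%, 75% | 37 | 0.030 |
| 10%, 100% | 40 | 0.079 |

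Only the last row loses significance. With 112 wire-crossed patients of whom 9 (8%) are not crossed by JS and all fail, leaving them out gives 22/103 (p = 0.004) and counting them gives 31/112 (p = 0.07). That case also needs q = 100%.

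**Near the boundary.** 38/140 is the highest significant count (p = 0.042); 39/140 gives p = 0.058. Turning 40/140 into 38/140 needs f = (2/140)/(q − 38/140), which is 13.3% at q = 37.9%, 6.3% at q = 50% and 2.0% at q = 100%.

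**False claim if JS is no better.** Set the rate in the wire-crossed set to 37.9%. The catheter-crossed rate is then (0.379 − fq)/(1 − f). Exact binomial enumeration of 140 against 182, rejecting at z < −1.96, gives:
- q = 37.9%: the crossed rate stays at 37.9% for any f, and the false-claim rate stays at 2.5%.
- f = 5%, q = 50%: crossed rate 37.3%, false-claim rate 3.3%.
- f = 5%, q = 100%: crossed rate 34.6%, false-claim rate 8.7%.

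**The case against.** The harm depends on one reading that fits poorly with other text. JS cuts as it advances, and section 12.0 defines a JS pass as travel from the proximal to the distal end of the lesion. Crossing with JS would therefore be treatment, and enrolment would follow it, against 4.4 and 4.62. Taking the treatment catheter as one placed before therapy reconciles every section. The Index Procedure definition in 12.0 also covers procedures that were only attempted. This stands as an argument about intent. It does not settle the matter, because the term is undefined and the plan calls its own device a catheter, so a site can reasonably follow 4.46 in the harmful sense.

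Four stronger conclusions that a reader might draw are not supported:

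- **That the result would be overturned.** This needs every non-crosser to fail and a non-crossing share of about 8% to 10%. Nothing in the documents suggests either. The JS and predecessor series in section 3.32 report no failed crossing, although they may include only treated cases.
- **That the missing ITT definition is a separate error.** In a single-arm study ITT ordinarily means all enrolled patients, and section 4.1 follows all subjects after enrolment. Settling the enrolment point settles most of it.
- **That bailout stents in non-crossers escape the endpoint even when those patients are enrolled.** The Adjunctive Treatment entry in 12.0 describes procedures after JS plus angioplasty, but it does not define bailout stenting. Section 4.2 governs and counts any intra-procedural bailout stent of the index lesion.
- **That the comparator is shown to be free of such removals.** The denominators of 57 and 81 match the arms in section 3.2, but the arm of 44 cannot be checked there, the counts are labelled as estimated, and the source trials' enrolment points are not given.

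**Conclusion.** The conflict is real and stands in operative text; the listed protocol changes do not touch it. Whether it biases anything depends on what the treatment catheter is. If it is the JS catheter, failed JS crossings leave both primary rates, and the JS rate is biased downward if those patients fail more often than the rest. If it is a catheter placed before therapy, there is only a wording conflict.

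The size cannot be fixed from the documents. On their own angioplasty rate for non-crossers the effect is small: at most 1.7 points at a 10% non-crossing share, with no inflation of the false-claim rate. The larger figures, up to 7.9 points and an 8.7% false-claim rate, rest on unsourced event rates and mark the outer range only. At the planned effect with 140 analysed, the conclusion survives every combination tried except f = 10% with q = 100%. The point is worth correcting because the text is contradictory, any bias would favour the device, and the remedy is cheap.

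**What to change.** - Reconcile sections 4.4, 4.46, 4.62, 4.641 and the Enrollment entry in 12.0 to one enrolment point that precedes introduction of the JS catheter. The guidewire-crossing point already in 4.62 serves.
- Delete the term treatment catheter, or define it.
- State in 5.23 that the ITT and 30-day MAE sets are all patients who reach that point, and describe the actual-treatment set separately.
- Add a CRF item recording whether JS crossed the lesion, and report the number of non-crossers and their events.

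The cost is protocol wording and one CRF item. Sample size, treatment and visits do not change. The downside for the sponsor is that a few early device failures will count against JS.
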